- CBC, platelets, creatinine, AST, ALT, and bilirubin will be monitored bi-weekly during administration (weeks 2, 4, and 6).
- Blood for immune research studies* (10 to 40 cc) may be collected in week 2-3 after the NSC-CRAd injection and 2-4 weeks after completion of radiation therapy
- MRI of the brain approximately 28 days after study product injection, 2-4 weeks after completion of radiation, and then every 2-3 months for the first year or until disease progression.
- If surgery is performed, tumor samples will be examined in conjunction with the pathologist and samples retained for future studies if consent given by the patient.
- Evaluation once a year for 5 years. Evaluations will include: Physical and neurological examination, MRI, and CBC with differential count.

Statistical Considerations:

Statistical analysis will be descriptive only, with no hypothesis testing. All the endpoint data will be collected and described in summary tables for both two arms at each dose. In general, descriptive statistics (n, mean, standard deviation, median, minimum, and maximum) will be presented for continuous variables. Frequencies and percentages will be calculated for categorical and ordinal variables at each category. All study data will be presented in by-subject data listings. Statistical analyses will be performed using SAS9.4 (SAS Institute Inc., Cary, NC).

The maximum tolerated dose (MTD) will be determined according to the dose escalation algorithm. If >2 patients do not complete the initial RT/TMZ phase or rule if > 2 patients experience life threatening or fatal neurologic toxicity, the trial will be stopped to analyze, in conjunction with the DMC, whether this regimen is tolerable.

Demographic (age, sex, height and weight) and baseline disease characteristics (including baseline KPS), will be summarized for both arms as well as the entire group. Kaplan-Meier curves and median survival estimates with confidence limits will be given for both overall survival and progression-free survival. The association of extent of immune response with overall survival will be determined by Cox's proportional hazards model.

Safety parameters will be analyzed descriptively, and presented in standard frequency tables (adverse events), shift tables (Laboratory parameters) and summaries of change from baseline over time (vital signs, physical examination, ECG and laboratory parameters).

Sponsor/Licensee:

Northwestern University/[name]

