4.9 Duration of Follow Up

Patients will have a follow-up visits days 1-3 while hospitalized, days 7, 14, and 28 after NSC-CRAd-S-pk7 administration and then at day 56, and every 8 weeks after until disease progression or patient withdrawal. They will be monitored for toxicities by physical exam and laboratory results through day 56. They will also undergo a brain MRI on day 28 and at day 56 to monitor for toxicity and disease progression, then every 8 weeks to monitor for disease progression. Survival status will be monitored until patient death or for up to 5 years.

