10.3.2 Description of Statistical Methods

10.3.2.1 General Approach

All study data will be presented in by-subject data listings. Statistical analysis will be descriptive only, with no hypothesis testing. All the endpoint data will be collected and described in summary tables for both two arms at each dose. In general, descriptive statistics (n, mean, standard deviation, median, minimum, and maximum) will be presented for continuous variables. Frequencies and percentages will be calculated for categorical and ordinal variables at each category. Statistical analyses will be performed using SAS9.4 (SAS Institute Inc., Cary, NC)

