10.3.3 Safety Analyses

Safety endpoints include adverse events (including serious adverse events), deaths, laboratory parameters, vital signs, physical examination and ECG.

All Adverse event will be coded by System Organ Class (SOC) and Preferred Term using Medical Dictionary for Regulatory Activities (MedDRA) dictionary, and will be presented in frequency tables (overall and by intensity [CTCAE grading]) by SOC. In tables showing the overall incidence of adverse events, subjects who experienced the same event on more than one occasion are counted only once in the calculation of the event frequency. Listings will be presented by subject for all adverse events as well as for serious adverse events, adverse events associated with death, and adverse events leading to discontinuation from the study, unanticipated problems involving risks to subject or others. The following information will be included: start date, stop date, severity, relationship, outcome, and duration. Deaths will be listed and summarized descriptively.

Laboratory data will be presented as summary statistics by dose group using both shift and frequency tables. For each continuous laboratory parameter, results will be categorized as low, normal or high based on the laboratory normal ranges. Subjects who had a shift to low and those who had a shift to high from baseline to any post-dosing assessment will be summarized. All out-of-range and clinically significant laboratory results will be identified in subject data listings.

Individual patient values of vital sign parameters including systolic and diastolic blood pressure and heart rate will be listed by patient. The absolute and percentage changes from baseline will be computed and potentially serious changes will be flagged. Appropriate summary statistics will be provided for all vital sign parameters.

The number and percentages of subjects in each dose group with normal and abnormal ECG performance status and physical examination results will be presented for evaluations at baseline and final visit. For each body system, changes in subjects' findings from baseline to final visit (no change, normal to abnormal, or abnormal to normal) will be tabulated for each dose group.

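### Section 10.3.3 summarises ECG and physical examination at baseline and an undefined final visit, so an abnormality that appears after injection and resolves is tabulated as no change

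*Combined protocol and SAP*

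**What the plan says.** Section 10.3.3 lists physical examination and ECG among the safety endpoints. It then states that ECG and "physical examination results will be presented for evaluations at baseline and final visit", and that for each body system "changes in subjects' findings from baseline to final visit (no change, normal to abnormal, or abnormal to normal) will be tabulated" by dose group. The final visit is not defined there or elsewhere.

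Two other places set a different rule:

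- For laboratory data, the same section says that patients with a shift to low or a "shift to high from baseline to any post-dosing assessment will be summarized".
- The Study Summary (Statistical Considerations) promises "summaries of change from baseline over time (vital signs, physical examination, ECG and laboratory parameters", so it names both of the measures at issue.

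On timing, Section 4.9 schedules visits through Day 28, "then at day 56, and every 8 weeks after until disease progression or patient withdrawal", and ends toxicity monitoring by physical examination at Day 56. Table 4 adds annual examinations for five years. Table 5 puts the physical examination and the targeted neurological examination in one row. Its ECG row has four marks and none at Day 28 or later.

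On other reporting, Section 10.3.2.1 says "All study data will be presented in by-subject data listings", and Section 10.3.3 says that adverse events "will be presented in frequency tables (overall and by intensity [CTCAE grading]) by SOC".

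**The concern.** Safety is a primary objective, and the product is injected once into the brain. In Section 8.1.10, the protocol's own account of an earlier adenoviral trial in recurrent brain tumours describes events below the highest dose level as transient and milder, with seizure and neurological worsening among them. A table that compares baseline with one late time point is poorly suited to findings of that kind: a change that comes and goes leaves no trace in it.

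For the physical examination there is a second problem. If the last examination is made when the tumour has progressed, the table can record disease status by dose group under the name of safety. A reader of the final report could then see no change for a patient with an early deficit that resolved, and a new abnormality for a patient whose only problem was progression.

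**Working it through.** No sample size, power or error rate bears on this point, and the plan gives no figure to reproduce. The check sets the rules and the visit schedule side by side.

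**Step 1: the rules.**

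| Measure | Section 10.3.3 | Study Summary |
|---|---|---|
| Laboratory | shift at any assessment after dosing | change over time |
| Physical examination | baseline and final visit | change over time |
| ECG | baseline and final visit | change over time |

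The Study Summary treats the three measures alike; Section 10.3.3 does not, and gives no reason for the difference.

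**Step 2: what each rule does with three simple courses.**

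| Baseline | Early after injection | Final visit | Final-visit rule | Any-assessment rule |
|---|---|---|---|---|
| normal | abnormal | normal | no change | shift counted |
| normal | normal | abnormal at progression | normal to abnormal | counted only if the window includes that visit |
| abnormal | worse | abnormal | no change | no change |

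The first row is the loss described above. The second shows why a worst-finding rule also needs an end date. The third is a limit of any normal/abnormal table, and changing the time point does not cure it.

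**Step 3: when the final physical examination can fall.** Visits recur every 8 weeks after Day 56, so the first one outside the toxicity window is at Day 56 + (8 × 7) = Day 112. They go on until progression or withdrawal, and Table 4 extends annual examinations to five years. An undefined final visit can therefore be Day 56, the progression visit, or an annual visit years later.

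**Step 4: when the final ECG can fall.** The extracted Table 5 may be displaced by one column, because its surgery mark lands on Day 1 although injection is on Day 0. Both readings were checked. As printed, the ECG marks are at screening, Day 0, Day 3 and Day 14. Shifted one column to the left, the last two fall on Day 2 and Day 7. Either way the last scheduled ECG is within about two weeks of injection. If that recording is taken as the final one, only an earlier post-injection change (around Day 2 to 3) can be masked. If final visit means a later study visit, no ECG is scheduled there at all.

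**Step 5: whether Day 56 is a sensible cut-off.** Section 4.6.2 starts radiation 10 to 14 days after injection and continues it for about six weeks, so it ends at about Day 10 + 42 = 52 to Day 14 + 42 = 56. A Day 56 window therefore matches the toxicity monitoring in Section 4.9 and covers roughly the DLT period of Section 4.2.1, unless treatment runs longer or is delayed.

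**The case against.** The strongest case on the other side has four parts.

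- **The texts may only need reconciling.** The Study Summary already promises summaries over time, and Section 10.3 says that a formal SAP with more detail will follow before database lock. This stands: the plan contains an inconsistency, not a settled choice of two time points. But the detailed analysis section holds the less informative rule, and a programmer would work from it.
- **Final visit might mean Day 56.** Toxicity monitoring by examination and routine adverse event reporting both end then. That reading is possible, and it would remove the progression problem. It would not restore a finding that resolved before Day 56.
- **Other reporting captures these events.** Section 7.2.1 makes any unfavourable sign an adverse event, including worsening of a pre-existing condition. Section 7.2.3 makes a significant new neurological deficit within 7 days after surgery serious. Section 4.2.1 judges neurological toxicity against pre-treatment status and requires safety review 14 days after the first and second subjects and before escalation. This stands and limits the weight of the point.
- **The remedy is not clean.** A worst finding through Day 56 will include effects of biopsy or craniotomy and, from Day 10 to 14, of RT/TMZ. This also stands and is accepted as a cost.

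Two stronger readings are tempting. A reader might infer that transient toxicity vanishes from the trial's safety reporting, or that the MTD is at risk. The documents do not support either: Section 10.3.2.2 determines the MTD from DLTs under the escalation algorithm, and the adverse event tables count an event whether or not it resolves. A reader might also infer that tumour progression contaminates the ECG table. The ECG schedule rules that out as the route.

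**Conclusion.** The point holds for this one summary table and is of minor to moderate weight. Section 10.3.3 conflicts with the Study Summary and applies a weaker rule to ECG and physical examination than to laboratory data. As written, the table hides a resolved post-injection abnormality for both measures. For the physical examination only, it can also draw its post-injection value from a visit at or after progression.

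The size cannot be computed, because the documents give no rate of transient findings and do not say how often the last visit is the progression visit. With 3 to 6 patients per dose level in each arm, the number of affected patients at a level could be anything from none to all of them.

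The conclusion rests on two assumptions: that Section 10.3.3 would be followed literally, and that its physical examination includes the targeted neurological examination. That section does not name the neurological examination, so the second assumption is inferred from the shared row in Table 5.

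**What to change.** Change Section 10.3.3, or write the rule into the formal SAP and correct the section to match:

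1. Tabulate, by arm and dose, the shift from baseline to the worst post-injection finding. For physical examination, do this by body system through Day 56 and state that the targeted neurological examination is included. For ECG, use its scheduled post-injection assessments.
2. Add a by-visit summary of both measures, as the Study Summary already promises.
3. Define the final visit, and keep the baseline-to-final table only as a supplement.
4. Clarify the wording that attaches performance status to ECG. It could mean an ECG result or a performance scale, and the protocol's scale is KPS.

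The cost is one or two more tables; no visit or measurement is added. The worst-finding table will mix product effects with those of surgery and RT/TMZ, so it should carry a note to that effect and be read beside the adverse event attribution. It will still not show worsening in a patient whose examination was already abnormal at baseline; the graded adverse event table remains the place for that.

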10.3.4 Baseline Descriptive Statistics

Demographic (age, sex, height and weight) and baseline disease characteristics (including baseline KPS), will be summarized for both arms.

11.0 STUDY MANAGEMENT

11.1 Institutional Review Board (IRB) Approval and Consent

It is expected that the IRB will have the proper representation and function in accordance with federally mandated regulations. The IRB should approve the consent form and protocol.

In obtaining and documenting informed consent, the investigator should comply with the applicable regulatory requirement(s), and should adhere to Good Clinical Practice (GCP) and to ethical principles that have their origin in the Declaration of Helsinki.

Before recruitment and enrollment onto this study, the patient will be given a full explanation of the study and will be given the opportunity to review the consent form. Each consent form must include all the relevant elements currently required by the FDA Regulations and local or state regulations. Once this essential information has been provided to the patient and the investigator is assured that the patient understands the implications of participating in the study, the patient will be asked to give consent to participate in the study by signing an IRB approved consent form.

Prior to a patient's participation in the trial, the written informed consent form should be signed and personally dated by the patient and by the person who conducted the informed consent discussion.

11.2 Amendments

The Principal Investigator will formally initiate all amendments to the protocol and/or informed consent. All amendments will be subject to the review and approval of the appropriate local, institutional, and governmental regulatory bodies.

11.3 Registration Procedures

11.3.1 Registering a Patient for the Phase I Portion of the Study

For potential patients for the phase I portion of this study, study teams are asked to inform the QAM of the date and time that the patient will need to be registered ([contact]).

BEFORE a patient can be treated on study, please complete and submit the following items to confirm eligibility and receive an identification number:

- Patient's signed and dated informed consent form (upload to NOTIS and keep original hard copy in a secure location/study chart)
- Eligibility checklist (signed and dated by the treating physician – upload to NOTIS)
- Eligibility eCRF (complete in NOTIS)
- Copy of the pathology report (upload to NOTIS)

The QAM will review all source documentation required to confirm eligibility that is readily available in the patient's electronic medical record (EMR). Any information that is not available in the EMR must be de-identified and emailed to the QAM. Once the QAM confirms the patient is eligible, he or she will register the patient, assign a subject identification number, provide a cohort assignment, and send a confirmation of registration to involved personnel. Registration will then be complete and the patient may begin study treatment.

11.3.2 Registering a Patient to the Phase II Portion of the Study

11.4 Data Submission

Once a subject is confirmed and registered to the study, eCRFs should be submitted according to the detailed data submission guidelines (provided in a separate document). All data for phase I patients during the time period patients are evaluated for Dose Limiting Toxicities (DLTs) must be submitted on a weekly basis.

11.5 Data Management and Monitoring/Auditing

This study will be conducted in compliance with the Data Safety Monitoring Plan (DSMP) of the Robert H. Lurie Comprehensive Cancer Center of Northwestern. The assigned QAM, with oversight from the Data Monitoring Committee, will monitor this study in accordance with the study phase and risk level. Please refer to the NOTIS for additional data submission instructions.

11.6 Adherence to the Protocol

Except for an emergency situation in which proper care for the protection, safety, and well-being of the study patient requires alternative treatment, the study shall be conducted exactly as described in the approved protocol.

11.6.1 Emergency Modifications

Investigators may implement a deviation from, or a change of, the protocol to eliminate an immediate hazard(s) to trial subjects without prior IRB approval.

For any such emergency modification implemented, an IRB modification form must be completed within 5 business days of making the change, and the QAM must be notified within 24 hours of such change.

11.6.2 Other Protocol Deviations

All other deviations from the protocol must be reported to the assigned QAM using the appropriate form.

A protocol deviation is any unplanned variance from an IRB approved protocol that:

- Is generally noted or recognized after it occurs.
- Has no substantive effect on the risks to research participants.
- Has no substantive effect on the scientific integrity of the research plan or the value of the data collected.
- Did not result from willful or knowing misconduct on the part of the investigator(s).

A protocol deviation may be considered an instance of Promptly Reportable Non-Compliance (PRNC) if it:

- Has harmed or increased the risk of harm to one or more research participants.
- Has damaged the scientific integrity of the data collected for the study.
- Results from willful or knowing misconduct on the part of the investigator(s).
- Demonstrates serious or continuing noncompliance with federal regulations, State laws, or University policies.

11.7 Investigator Obligations

The Principal Investigator is responsible for the conduct of the clinical trial at the site in accordance with Title 21 of the Code of Federal Regulations and/or the Declaration of Helsinki. The PI is responsible for personally overseeing the treatment of all study patients. The PI must assure that all study site personnel, including sub-investigators and other study staff members, adhere to the study protocol and all FDA/GCP/NCI regulations and guidelines regarding clinical trials both during and after study completion.

The Principal Investigator at each institution or site will be responsible for assuring that all the required data will be collected, entered onto the appropriate eCRFs, and submitted within the study-specific timeframes. Periodically, monitoring visits may be conducted and the Principal Investigator will provide access to his/her original records to permit verification of proper entry of data. The study may also be subject to routine audits by the Audit Committee, as outlined in the DSMP.

11.8 Publication Policy

All potential publications and/or data for potential publications (e.g. manuscripts, abstracts, posters, clinicaltrials.gov releases) must be approved in accordance with the policies and processes set forth in the Lurie Cancer Center DSMP. For trials that require high intensity monitoring, the assigned QAM will prepare a preliminary data summary (to be approved by the DMC) no later than 3 months after the study reaches its primary completion date (the date that the final subject is examined or receives an intervention for the purposes of final data collection for the primary endpoint). If the investigator's wish to obtain DMC-approved data prior to this point (or prior to the point dictated by study design), the PI must send a written request for data to the QAM which includes justification. If the request is approved, data will be provided no later than 4 weeks after this request approval. The data will be presented to the DMC at their next available meeting, and a final, DMC-approved dataset will be released along with any DMC decisions regarding publication. The investigators are expected to use only DMC-approved data in future publications. The investigators should submit a copy of the manuscript to the biostatistician to confirm that the DMC-approved data are used appropriately. Once the biostatistician gives final approval, the manuscript may be submitted to external publishers.

References

Appendix A. iRANO criteria	
Term	Criteria
Complete Response (CR)	The enhancing tumor is no longer seen by neuroimaging, with the patient off all steroids, or on adrenal maintenance only.
Partial Response (PR)	Decrease of $\geq 50\%$ in the product of two diameters with the patient on a stable or decreasing dose of steroids, with a stable or improving neurologic examination for at least six weeks.
Minor Response (MR)	Decrease in diameter products of $< 50\%$ with the patient on a stable or decreasing dose of steroids, with a stable or improving neurologic examination for at least six weeks.
Stable Disease (SD)	The scan shows no change. Patients should be receiving stable or decreasing doses of steroids.
Progression (P)	Increase of $> 25\%$ in tumor area (two diameters) provided that the patient has not had his/her dose of steroids decreased since the last evaluation period. A concomitant decrease in steroid dose will rule out a progression designation during the first two months after completion of radiation
Pseudoprogression (PP)	Radiological changes without concomitant neurological changes. It is not unusual to see enhancement in the context of oncolytic viral therapies. If thought to be the case, serial MRI imaging is warranted.

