6.2 Secondary Endpoints

This phase 1 study is not powered to detect statistically significant differences in efficacy.

However, data will be collected and described descriptively on the following endpoints:

- objective tumor response: objective response to therapy as determined by iRANO criteria (table 9)
- overall survival : time from study project injection to death
- progression-free survival : time from study project injection to first confirmed disease progression as determined by objective tumor response
- quality of life: summary score on patient self-report measure, Functional Assessment of Cancer Therapy- Brain component (as determined by patient self-report on FACT-Br v4, appendix C)

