10.2 Sample Size and Accrual

This phase 1 study is not powered to detect statistically significant differences in efficacy. The primary endpoint of this Phase I dose-escalation study is the MTD of NSC-CRAd-S-pk7 when administered with standard radiation and chemotherapy in patients with malignant glioma. The 3+3 design has a 71% chance (49%, 17%) of dose escalating when the true toxicity rate for that dose is 20% (30%, 50%).

If all three dose levels are administered, the minimum number of patients enrolled will be 9 per arm and the maximum number of patients will be 18 per arm, for total accrual of 18-36 patients enrolled. Based upon the dose escalation schema described, groups of three to six patients will be entered at a dose level in each arm. Using this algorithm, the probabilities of dose escalation for various true DLT rates are given in Table 10. For example, if the true DLT is 50% at a dose level, there is a 17% chance that the dose would be escalated. The maximum tolerated dose determined in this study will be the recommended dose for a Phase II study. In the event the final pathology reading reveals anything other than a malignant glioma, such a patient will not be counted as one of the minimum number required without DLT for advancement to the next dose level but will be counted if a DLT is experienced.

Table 10– Probabilities of Dose Escalation	
20%	71%
30%	49%
40%	31%
50%	17%
60%	8%

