10.3.2.3 Analysis of the Secondary Endpoint(S)

For objective tumor response, a summary table will be produced to present the number and proportion of responders in each arm, together with each of the response categories, namely CR, PR, MR, SD, P and PP.

The analysis of overall survival and progression-free survival are based on the survival function, estimated by the Kaplan-Meier method. Survival will be calculated from the day of study inclusion until progression and death, respectively, or will be censored at the date of last available follow-up information. The survival function will be summarized for 25th percentile, median, and 75th percentile, and the survival curves of the two arms will be presented.

Descriptive statistics will be used to describe the overall quality-of-life score on physical well-being, social/family well-being, emotional well-being, functional well-being and additional concerns, respectively.

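### Appendix A sets a neurologic condition with a six-week period for PR and MR but not for CR, so one scan in a neurologically worsening patient can count as complete response

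*Combined protocol and SAP*

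**What the plan says.** Appendix A gives the response categories. CR rests on imaging and steroid status alone: "The enhancing tumor is no longer seen by neuroimaging, with the patient off all steroids, or on adrenal maintenance only". PR needs a decrease of at least 50% "in the product of two diameters with the patient on a stable or decreasing dose of steroids, with a stable or improving neurologic examination", and the sentence ends with a period of at least six weeks. MR, a decrease of less than 50%, carries the same steroid wording and the same closing clause: "with a stable or improving neurologic examination for at least six weeks".

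Section 6.2 makes objective response a secondary endpoint scored by these criteria. It mentions confirmation for progression only, in the definition of progression-free survival: "time from study project injection to first confirmed disease progression as determined by objective tumor response".

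Section 10.3.2.3 then says that "a summary table will be produced to present the number and proportion of responders in each arm, together with each of the response categories". It does not define a responder, does not say which assessment is tabulated, and has no confirmation rule. Section 10.3.2.1 makes all analysis descriptive. Section 10.3 defers further detail to a separate SAP due before database lock, which is not among the documents.

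**The concern.** The protocol treats a neurologic examination that is no worse as part of what makes PR or MR credible, then leaves it out of the category above them. Nor does CR have any period over which the finding must hold. Two kinds of patient could therefore enter the table as complete responders: one who is clinically declining when enhancement disappears, and one whose enhancement is absent on one scan and present on the next.

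At stake is the meaning of the CR count and, if responder includes CR, of the responder proportion in each arm. The arms are small, so one patient shows. The trial is also open label, so a rule settled after the scans have been read would invite case-by-case judgement.

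**Working it through.** **Conditions side by side (Appendix A)**

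| Category | Imaging | Steroids | Neurologic condition | Period |
|---|---|---|---|---|
| CR | no enhancing tumor | none, or adrenal maintenance only | none | none |
| PR | decrease of 50% or more | stable or falling | no worse | six weeks |
| MR | decrease under 50% | stable or falling | no worse | six weeks |
| SD | no change | stable or falling | none | none |
| P | area up by more than 25% | not decreased since last evaluation | none | none |

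Pseudoprogression (PP) is for radiological change without neurologic change.

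**Literal application**

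- Patient 1 is off steroids, shows no enhancement at Day 112, has a worse examination, and has enhancement again at Day 168. At Day 112 every CR condition is met, so the patient is CR.
- Patient 2 has a 90% decrease at Day 112 on a stable steroid dose, with the same worse examination. PR fails on the examination. MR fails on the examination and on size. SD fails because the scan has changed, P because the area has not grown, and PP because there is neurologic change. No category fits.
- If CR carried the neurologic condition, patient 1 at Day 112 would be where patient 2 is: in no category. A repair therefore has to name a place for such patients.

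**What the six weeks govern.** In PR and MR the period follows the examination, so it may apply to the examination alone or to the whole response. On the first reading PR and MR need no second scan either, and the secure difference from CR is the neurologic condition and its duration. On the second reading CR also lacks a persistence requirement that the others have.

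**Size.** The plan states no response rate, so there is no figure to reproduce. The denominator comes from section 10.2, if all three dose levels are given: "the minimum number of patients enrolled will be 9 per arm and the maximum number of patients will be 18 per arm". One patient scored CR under the present wording, but not under the repaired one, changes the arm's proportion by

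- 1/9 = 11.1 percentage points at the minimum;
- 1/18 = 5.6 percentage points at the maximum.

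Section 10.3.2.1 also calls for summaries by arm at each dose. With 3 to 6 patients per dose (section 4.2), one patient is 1/3 = 33.3 to 1/6 = 16.7 points.

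**Can scheduled scans support a persistence rule?** Section 4.9 has brain MRI at Days 28 and 56 and then every 8 weeks.

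- Day 28 to Day 56: 28 days, short of 42.
- Day 56 to Day 112, and each later pair: 56 days, more than 42.

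A finding at Day 56 or later can be checked at the next scheduled scan; a Day 28 finding would be checked at Day 112. Table 4 gives a different interval, every two to three months in the first year, which also exceeds six weeks.

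**The case against.** Several points on the other side are sound.

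- CR has the strictest steroid condition in the table. That guards against disappearance produced by steroids, though not against neurologic decline or an unsustained reading.
- The six-week clause may govern the examination only, so a short-lived 50% decrease with a stable examination might also score PR on one scan. This stands. It limits the CR-specific part of the point to the neurologic condition and makes a common persistence rule the right remedy.
- Response is secondary, the study is not powered for efficacy, and nothing is tested. Each category is tabulated and all data are listed by subject, so an unsustained CR could be traced. This lowers the consequence but does not correct the classification.
- The later SAP could define responder and confirmation. That is an opportunity; the rule now in force is Appendix A.

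A reader might infer that the criteria are upside down, with the top category the easiest to reach. They are not: CR demands complete disappearance of enhancement and the tightest steroid status, and SD also has no duration or neurologic clause.

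A reader might also want a probability that a patient picks up a false CR over a year of scans. The documents do not support one. They give no frequency of transient non-enhancement and do not say that the best response ever seen is what is tabulated. Eight-weekly scanning stops at progression or withdrawal.

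**Conclusion.** The point holds in limited form. Appendix A omits from CR the neurologic condition that it sets for PR and MR, and no other section supplies it. CR also has no stated duration; whether PR and MR require the response itself to last is ambiguous.

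The consequence is a possible upward bias in the CR count and the responder proportion: 5.6 to 11.1 points per arm for each affected patient. This assumes that responder includes CR and that 9 to 18 patients per arm form the denominator. How many patients would be affected cannot be derived from the documents, so inflation is a risk and not a demonstrated result. The MTD does not depend on response and is unaffected. The repair is worth making before results are known.

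**What to change.** 1. In the CR row of Appendix A, add the neurologic condition already written for PR and MR.
2. State whether the six weeks apply to the examination only or to the whole response, and apply one persistence rule to CR, PR and MR. For example: the finding still holds at the next scheduled MRI at least six weeks later.
3. Add a named category, such as unconfirmed/not classifiable, for disappearance or shrinkage that fails these conditions, and count it as non-response. Without it such a patient may fit none of PR, MR, SD or P.
4. Define responder in section 10.3.2.3 to match, including which categories count and which assessment is tabulated.

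The cost is wording in Appendix A and section 10.3.2.3. On the section 4.9 schedule no scan or examination is added. A finding on a patient's last scan would stay unconfirmed, and the reported CR and response proportions may be slightly lower.
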